Baseline Visit (Day -1): Subjects who meet eligibility criteria at Screening will return to the study site on Day -1 for confirmation of screening evaluations as well as completion of predose assessments and procedures including clinician review of the daily binge eating diary. Any lapse in diary completion during the 14 day period (eg, 1 or more days are skipped) will be discussed with the subject. If 1 or 2 days per week are incomplete or missing, the subject may complete the diary with the clinician. However, if the subject cannot recall enough information to complete the diary in full after clinician review, the subject will be ineligible. Subjects will also be ineligible for randomization if there are more than 2 missed diary days in 1 week. Eligible subjects (based on confirmation of study entry criteria) will be randomized and dispensed study drug at Day -1.

Treatment Period (Day 1 [Week 0] through Day 84 [Week 12]): Subjects will self-administer the study drug on an outpatient basis once a day with or without food beginning on Day 1, the day after the Baseline visit, and continue for 12 weeks. Subjects will be instructed to administer study drug at approximately the same time each morning including on days when clinic visits occur. During the treatment period subjects will continue to complete a daily binge eating diary, which will be reviewed at each visit. During the treatment period, subjects will have one clinic visit every week for the first month, then one clinic visit every 2 weeks thereafter. In order to facilitate scheduling of clinic visits, a window of ± 2 days will be allowed for each weekly clinic visit and a window of ± 3 days will be allowed for each biweekly clinic visit, and a window of ± 1 day for the end of treatment (EOT) visit and each clinic visit of the withdrawal period.

Subjects who complete the 12-week Treatment Period may be eligible for participation in the open label extension study (SEP360-322). For subjects enrolling in the open label extension study, Week 12 will be the last visit for this study.

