15.4.1. Efficacy Analyses

15.4.1.1. Assessments from Binge Eating Diary

The number of binge days per week at each assessment timepoint will be derived based on clinician review of the binge eating diary collected in the time intervals as follows:

- Baseline: binge eating diary completed for 14 consecutive days immediately prior to the Baseline visit and starting no sooner than the day after the screening visit;

- Weeks 1, 2, 3, and 4 (ie, Visits 3, 4, 5, and 6): binge eating diary collected at each visit, which will span from the previous visit to the current visit and therefore cover Weeks 1, 2, 3, and 4, respectively;
- Weeks 6, 8, 10 and 12 (ie, Visits 7, 8, 9, and 10): binge eating diary collected at each visit, which will span from the previous visit to the current visit and therefore cover Weeks 5/6, 7/8, 9/10, and 11/12, respectively.

Specifically, the number of binge eating days per week at baseline is calculated as the number of binge eating days in the 14 days immediately prior to the Baseline visit multiplied by 7 and divided by the number of days in the Baseline period (ie, 14 days); the number of binge days per week in a visit that spans between 2 scheduled visits is calculated as (total number of binge days) x 7 / (total number of assessed days in the visit span). If missing diary entries exist during an assessed period for a subject, the available non-missing diaries from the subject will be used to derive the number of binge days per week adjusted by the number of non-missing diary days accordingly.

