5.1. Efficacy Variables

5.1.1. Variables Derived Per Binge Eating Diary

All binge episodes will be captured daily by the subject in a binge eating diary using paper format to record the date, duration (total hours of binging), type of binge episode (meal or non-meal), amount and type of food, and number of binges. The number of binge days per week and the number of binge episodes per week at each assessment timepoint will be derived based on clinician review of the binge eating diary collected in the time intervals as follow:

- Baseline: binge eating diary completed for 14 consecutive days immediately prior to the Baseline visit;
- Weeks 1, 2, 3, and 4 (ie, Visits 3, 4, 5, and 6): binge eating diary collected at each visit, which will span from the previous visit to the current visit and therefore cover Weeks 1, 2, 3, and 4, respectively; Particularly, Week 1 visit period will span from Day 1 (ie, 1st dose day) to one day before Week 1 visit date (inclusive).
- Weeks 6, 8, 10 and 12 (ie, Visits 7, 8, 9, and 10): binge eating diary collected at each visit, which will span from the previous visit to the current visit and therefore cover Weeks 5/6, 7/8, 9/10, and 11/12, respectively.
- Withdrawal Weeks 1, 2, 3 (ie, Week 13, 14, and 15): binge eating diary collected at each withdrawal visit, which will span from the previous visit to the current visit and therefore cover Visits 11, 12, and 13, respectively.

Specifically, the diary information collected on the post-DB baseline visits will be counted into the corresponding week span; for an example, diary collected on Week 1 visit data will be counted into the diary data at Week 1; diary collected on Week 2 visit data will be counted into the diary data at Week 2; and so on.

Diary records reviewed at early termination visit will be mapped into scheduled visit. Mapping rule of early terminated visit for binge eating diary based on study day is provided in [Section 6.1.4.1](#).

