For very rare situations, a subject might miss a scheduled visit and come back at the next scheduled visit. For such a case, diary records are expected to be collected continuously without interruption. The collected diary will be reviewed on the next scheduled visit. During the double-blind treatment period, if a diary contains binge eating diary records for a missed visit, the diary records will be split into two parts by using the target day of the missed visit (see Table 2 in study protocol) as a data cut: part 1 starts from the previous scheduled visit date (inclusive)

321

to the target day of the missed visit (exclusive), and part 2 starts from the target day of the missed visit (inclusive) to the current visit (exclusive). Part 1 and Part 2 data will be used to derive binge diary related variables for previous scheduled visit and the missed visit, respectively.

5.1.1.1. Number of Binge Days, Number of Binge Episodes, and Number of Assessed Days During a Visit Period

Number of assessed days at baseline will be 14 days. The number of binge eating days per week at baseline is calculated as the number of binge eating days in the 14 days immediately prior to the Baseline visit multiplied by 7 and divided by the number of days in the Baseline period. No missing diary entry is expected. In case there is a missing diary, the non-missing diary days in 14 days immediately before randomization will be used to derive these variables.

For each post-baseline assessment visit defined in [Section 5.1.1](#),

- Number of assessed days within the visit period is defined as the difference in study day between the current visit and the previous visit (ie, study day of current visit – study day of previous visit). If missing diary entries exist during the assessed period for a subject, the number of assessed days will be derived based on the days with non-missing diaries.
- Number of binge days is counted as the binge days that occur between the previous visit date (inclusive) and a day before the current visit date (inclusive).
- Number of binge episodes is counted in a similar way. If missing diary entries exist during the assessed period for a subject, number of binge days and number of binge episodes will be derived based on the days with non-missing diaries.

5.1.1.2. Number of Binge Days per Week and Number of Binge Episodes per Week for a Visit Period

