6.1.1.1. Double-Blind Treatment Period (On Treatment)

The double-blind treatment period will begin with the day when the first dose of double-blind study medication is taken, which will be denoted as study Day 1. The end of the double blind phase is defined as the maximum of the last date of administration of study medication and the withdrawal completion date of the treatment period (ie, Week 12/EOT visit date). If the end date of the medication intake is unknown (eg, subject is lost to follow-up), the end of the double blind period is defined as the withdrawal date provided by investigator site. If a subject does not take any study medication, start and end of the treatment period are set to missing.

The start and end of treatment period are given below:

- **Start of treatment period** = Date/time of the first study medication administration during the double-blind treatment period
- **End of treatment period** = maximum of the last date of administration of study medication and the withdrawal/ completion date (ie, Week 12/EOT visit date)

Each subject's assessment at each visit in pre-treatment and treatment period will be assigned a study day with respect to start date of the treatment period.

- Study Day = Assessment date – start date of the treatment period + 1; if assessment date \geq start date of the study period
- Study Day = Assessment date – start date of the treatment period; if assessment date $<$ start date of the study period

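### The SAP's assessed-days formula gives a denominator of 8 for a Week 1 diary period that holds 6 days

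*SAP*

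**What the plan says.** **Denominator (SAP 5.1.1.1).** For each post-baseline visit, "Number of assessed days within the visit period is defined as the difference in study day between the current visit and the previous visit". No exception is made for Week 1. If entries are missing, "the number of assessed days will be derived based on the days with non-missing diaries".

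**Numerator (SAP 5.1.1.1).** It counts "the binge days that occur between the previous visit date (inclusive) and a day before the current visit date (inclusive".

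**Week 1 period (SAP 5.1.1).** A separate sentence says that "Week 1 visit period will span from Day 1 (ie, 1st dose day) to one day before Week 1 visit date (inclusive". Further on, the same section says "diary collected on Week 1 visit data will be counted into the diary data at Week 1".

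**Rate (SAP 5.1.1.2).** Binge days (or episodes) times 7, divided by assessed days, with both counts taken as defined in 5.1.1.1.

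**Study days.** Under SAP 6.1.1.1, dates before the first dose use "Study Day = Assessment date – start date of the treatment period; if assessment date" precedes that start; dates on or after it add 1. Day -1 is thus followed directly by Day 1. The Baseline visit is on Day -1, and Protocol 7.1 has dosing "beginning on Day 1, the day after the Baseline visit, and continue for 12 weeks".

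**Protocol 15.4.1.1.** There is no subtraction rule. The rate is divided by the assessed days in the visit span, and when entries are missing "the available non-missing diaries from the subject will be used to derive the number of binge days per week", adjusted to the non-missing days.

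**The concern.** Subtracting study days counts calendar days correctly only when both days lie on the same side of the first dose. From Baseline to Week 1 the subtraction crosses from Day -1 to Day 1 and counts one day that does not exist. The Week 1 sentence in 5.1.1 also removes the Baseline visit day from the period. The denominator is therefore one day larger than the general numerator span and two days larger than the Week 1 period.

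Change in binge days and change in binge episodes at Week 1 are listed other secondary endpoints. The same Week 1 value is a response in the primary MMRM. It also feeds the by-visit flag for a reduction of at least 75%, the LOCF value of anyone whose last diary period is Week 1, and the binomial trial count if the GLMM is run. Early terminators whose last scheduled visit was Baseline are mapped to Week 1 by SAP Table 5, so the rule reaches them too.

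A complete diary does not trigger the missing-entry clause, so complete and incomplete Week 1 diaries end up on different scales.

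**Working it through.** The plan prints no Week 1 day count, so there is no figure to reproduce. The inputs are the Baseline visit on Day -1, the Week 1 visit on Day 7 (window Day 5 to Day 9), later visits on Days 14, 21, 28, 42, 56, 70 and 84, and no Day 0.

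**1. On-target Week 1 visit, complete diary**
- Subtraction: 7 - (-1) = 8.
- Week 1 period, Days 1 to 6: 6 days.
- General numerator rule, Day -1 plus Days 1 to 6: 7 days.

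The text therefore supports three pairings:
- 6/6, if the Week 1 period governs both parts.
- 7/8, if the general rules govern both parts.
- 6/8, if the Week 1 period governs the numerator and the subtraction governs the denominator.

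**2. Later visits as a control.** Subtraction gives 7, 7, 7, 14, 14, 14 and 14 for Weeks 2, 3, 4, 6, 8, 10 and 12. The calendar count from the previous visit to the day before the current one gives the same. At Week 12, 84 - 70 = 14. The mismatch is confined to Week 1.

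**3. Across the Week 1 window.** For a visit on Day v, the factors are (v-1)/(v+1) and v/(v+1):

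| Visit day | Subtraction | Week 1 period | Factor | General span | Factor |
|---|---|---|---|---|---|
| 5 | 6 | 4 | 0.67 | 5 | 0.83 |
| 6 | 7 | 5 | 0.71 | 6 | 0.86 |
| 7 | 8 | 6 | 0.75 | 7 | 0.875 |
| 8 | 9 | 7 | 0.78 | 8 | 0.89 |
| 9 | 10 | 8 | 0.80 | 9 | 0.90 |

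Reading the last column as a scaling of the Week 1 rate assumes that Day -1 has the same binge rate as the treatment days. For an early termination visit on Day 3 mapped to Week 1, the first factor is 2/4 = 0.50.

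**4. One subject.** Take four binge days in a complete Days 1 to 6 diary.
- Over 6 days: 4 x 7/6 = 4.67 per week.
- Over the subtraction: 4 x 7/8 = 3.50.
- If one non-binge day is missing, the denominator becomes 5 diary days: 4 x 7/5 = 5.60.

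One blank non-binge day thus moves the literal score from 3.50 to 5.60. With a consistent span it would move from 4.67 to 5.60.

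**5. Arm difference and responder flag.** At 6/8, a true difference of -1.0 reads -1.0 x 0.75 = -0.75. The flag for a reduction of at least 75% is met at a true reduction of 1 - 0.25/0.75 = 66.7%, or 1 - 0.25/0.875 = 71.4% at 7/8.

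**6. Effect at Week 12.** This was simulated with 200 trials of 160 per arm.
- From the plan: Week 12 effects of -0.9 and -0.8.
- Assumed: baseline mean 4.7 days per week, 37% dropout, and 10% of subjects with a missing Week 1 entry.
- Model: maximum likelihood MMRM with unstructured covariance and no center or stratum terms.

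| Result, 6/8 against 6/6 | Size |
|---|---|
| Shift in Week 12 difference, 6 mg | mean 0.002, largest 0.03 |
| Shift in Week 12 difference, 4 mg | mean 0.001, largest 0.03 |
| Week 1 difference, 6 mg | -0.47 becomes -0.37 |
| Placebo Week 1 change | -1.26 becomes -2.04 |

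**The case against.** The best defence is that the SAP already has a Week 1 rule. The sentence in 5.1.1 singles out Week 1, 5.1.1.1 refers to days within the visit period, and 5.1.1.2 divides by days in the visit span. A specific rule read over a general one gives 6/6 and no bias. I agree that this is probably what was meant. It does not repair the text: that sentence defines a period, the rate formula takes its counts from 5.1.1.1, and 5.1.1.1 defines assessed days by subtraction at every post-baseline visit.

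It is also fair that 6/8 mixes two rules and is the worst case. The consistent general reading, 7/8, is milder, but it puts a pre-dose day into an on-treatment rate and so contradicts 5.1.1. The documents do not show which version was programmed.

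The visit-day sentence in 5.1.1 may only say which visit a collected diary belongs to, and the numerator rule in 5.1.1.1 excludes the visit day. I treat that sentence as loose wording and rest nothing on it.

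The reach is limited, and that stands. The Week 1 endpoints are outside the fixed testing sequence, LOCF ANCOVA is supportive, the GLMM is conditional on model problems, and 4-week cessation does not use this denominator. The simulation is one scenario and leaves out the REML estimation and the center and stratum terms of SAP 7.2.3.2.1. It supports a negligible Week 12 effect, not an exact figure.

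**Conclusion.** The point holds. For a complete diary and an on-target visit, the stated subtraction gives 8 where the SAP's own spans hold 6 or 7 days, so it is wrong under every reading. If it is programmed as written, complete-diary Week 1 rates fall to 0.75 of their value with the Week 1 period in the numerator, or to about 0.875 with the general rule. The range is 0.67 to 0.90 across the visit window. The same rule applies in all arms, so it overstates the within-arm Week 1 change and tends to attenuate a between-arm difference; it does not create one. The Week 12 rate itself is computed correctly, and under the stated assumptions the effect on the primary comparison is negligible. The day counts rest only on the documents. Whether the bias occurs depends on code that the documents do not show. The text should be corrected, but the primary conclusion is not at risk.

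**What to change.** - In SAP 5.1.1.1, replace the subtraction with a count: assessed days are the non-missing diary days in the same span as the numerator. This agrees with Protocol 15.4.1.1.
- For Week 1, start numerator and denominator at Day 1 and end both on the day before the visit. With a complete diary the count is the visit study day minus 1, which is 6 on target.
- State that the Day -1 entry belongs to neither the baseline period nor the Week 1 period.
- Reword the visit-day sentence in 5.1.1 so that it matches the numerator rule.
- Check the derivation code against the revised text, including early termination visits mapped to Week 1.

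The cost is a few SAP sentences and a code check. No new data are needed.

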5.1.2. Binge-eating Clinical Global Impression-Severity (BE-CGI-S)

The BE-CGI-S is a single value, clinician-rated assessment of illness severity, and 7-point scale with range from 1 = normal, not at all ill; 2 = borderline mentally ill; 3 = mildly ill; 4 = moderately ill; 5 = markedly ill; 6 = severely ill; 7 = among the most extremely ill subjects. A higher score is associated with greater illness severity.

BE-CGI-S score is collected at Baseline, Weeks 2, 4, 6, 8, 10, and 12/EOT for randomized subjects, and at Week 15 for subjects who enter into the withdrawal period.

5.1.3. Yale-Brown Obsessive Compulsive Scale Modified for Binge Eating (Y-BOCS-BE)

Yale Brown Obsessive Compulsive Scale Modified for Binge Eating (Y-BOCS-BE) is a clinician-rated scale that measures the obsession of binge eating, thoughts and compulsiveness of binge eating behaviors. 10 questions are included in this assessment.

1. Time occupied by obsessive thoughts to binge eat
2. Interference due to thoughts to binge eat
3. Distress associated with thoughts to binge eat
4. Resistance of thoughts to binge eat

321

5. Degree of control over obsessive thoughts to binge eat
6. Time spent on compulsive behaviors to binge eat
7. Interference due to binge eating
8. Distress associated with binge eating
9. Resistance
10. Degree of control over binge eating

The 10-item scale, is rated from 0 (no symptoms) to 4 (extreme symptoms). Total scores range from 0 to 40. A score of 0-7 is sub-clinical; 8-15 is mild; 16-23 is moderate; 24-31 is severe; and 32-40 is extreme.

Y-BOCS-BE is divided into 2 subscales: obsessions and compulsions. The Y-BOCS-BE obsessions subscale is calculated as the sum of raw scores from obsessions questions (questions 1 to 5); and the subscale score ranges from 0 to 20. The compulsions subscale is calculated as the sum of raw scores from compulsions questions (questions 6 to 10); and the subscale score ranges from 0 to 20. Higher values of Y-BOCS-BE score and subscale scores represent greater severity of illness.

If there are any missing responses on the YBOCS-BE, the total score and corresponding subscale score are set as missing. Y-BOCS-BE score is collected at Baseline, Weeks 2, 4, 6, 8, 10, and 12/EOT for randomized subjects, and at Week 15 for subjects who enter the withdrawal period.

5.1.4. Eating Disorder Examination Questionnaire (EDE-Q) and Eating Disorder Examination Questionnaire (EDE-Q) Modified

The Eating Disorder Examination Questionnaire (EDE-Q) is a self-report version of the eating disorder examination (EDE) (Fairburn-1994). Like the EDE, the EDE-Q measures eating-disorder psychopathology in the past 28 days and over longer intervals for diagnostic items. EDE-Q generates two types of data. First, it provides frequency data (ie, numerical data) on key behavioral features of eating disorders in term of number of episodes of the behavior and in some instance number of days which behavior has occurred; Second, they provide ratings (ie, categorical data), 4 subscale scores, and a EDE-Q global score reflecting the severity of aspects of the psychopathology of eating disorders. The 4 subscale scores are Restraint, Eating Concern, Shape Concern, and Weight Concern. Severity rating ranges 0- 6, where 0 represents absence of the feature and 6 represents an extreme degree. Frequency ratings range from 0 to 6 where 0='No days' or absence of the feature, 6='every day'.

Both of the Eating Disorder Examination Questionnaire Brief Version (EDE-Q7) and EDE-Q modified (EDE-QM) are brief versions of the EDE-Q. EDE-Q7 was used in study SEP360-221 while EDE-QM is used in this study (SEP360-321).

EDE-Q7 comprises 7 items to generate a global score and 3 subscale scores (Restraint, Shape Concern, and Weight Concern). The EDE-Q7 along with 3 items (see below) to assess binge eating, including the number of binge eating days, is referred to as the EDE-Q modified.

321

- **Item 4:** Over the past 28 days, how many **times** have you eaten what other people would regard as an **unusually large amount of food** (given the circumstances)?
- **Item 5:** On how many of these times did you have a sense of having lost control over your eating (at the time that you were eating)?
- **Item 6:** Over the past 28 days, on how many **DAYS** have such episodes of overeating occurred (i.e., you have eaten an unusually large amount of food **and** have had a sense of loss of control at the time)?

See [Table 1](#) below for definition of rating data for EDE-Q, EDE-Q7, EDE-Q modified, and their relationship. [Table 2](#) provides the definition of frequency data for EDE-Q, EDE-Q modified, and their mapping relationship.

Table 1: Rating Data of EDE-Q , EDE-Q7, and EDE-Q modified Items

EDE-Q Modified Item	EDE-Q7 Item	EDE-Q Item	Abbreviated Content	Subscale
1	1	1	Restraint over eating	Restraint
		2	Avoidance of eating	
2	2	3	Food avoidance	
3	3	4	Dietary Rules	
		5	Empty stomach	
		7	Preoccupation with food, eating or calories	Eating Concern
		9	Fear of losing control over eating	
		19	Eating in secret	
		21	Social eating	
		20	Guilt about eating	
		6	Flat stomach	Shape Concern
		8	Preoccupation with shape or weight	
8	5	23	Importance of shape	
		10	Fear of weight gain	
10	7	26	Dissatisfaction with shape	
		27	Discomfort seeing body	
		28	Avoidance of exposure	
		11	Feelings of fatness	
7	4	22	Importance of weight	Weight Concern
		24	Reaction to prescribed weighing	
		8	Preoccupation with shape or weight	
9	6	25	Dissatisfaction with weight	
		12	Desire to lose weight	

321

[Reference: Fairburn C.G., 2014, EDE Edition 17.D, Cognitive Behavior Therapy and Eating Disorders\[1\]](#)

Table 2: Frequency Data of EDE-Q and EDE-Q modified Items

EDE-Q Modified Item	EDE-Q Item	Abbreviated Content
4	13	Times of unusually large amount of food
5	14	Times of having lost control eating
6	15	Days of overeating episodes
	16	Times of having made of sick for controlling shape or weight
	17	Times of having taken laxatives for controlling shape or weight
	18	Times of having exercised in a “driven” or “compulsive” for controlling shape or weight

For EDE-Q, EDE-Q Modified, and EDE-Q7, the subscale scores are calculated as average of the corresponding individual scores. If any individual score of the subscale is missing, the corresponding subscale score will be set as missing and no imputation will be done. An EDE-Q global score is calculated as average of 4 EDE-Q subscale scores. An EDE-Q7 global score is calculated as average of 3 EDE-Q7 subscale scores, and an EDE-Q modified global score is calculated as average of 3 EDE-Q modified subscale scores. The EDE-Q global score, EDE-Q modified global score, and EDE-Q7 global score will be missing if any of corresponding subscale score is missing. For EDE-Q, EDE-Q modified, and EDE-Q7, higher scores of the global score and subscale scores indicate greater levels of symptomatology. The global scores and subscale scores of EDE-Q modified and EDE-Q7 are equivalent.

EDE-Q is collected only at screening visit. EDE-QM is collected at Baseline and Week 12/EOT. Both EDE-Q and EDE-QM are designed to collect the data in the past 28 days; for a subject who is early terminated from the treatment period, these questionnaires may not be appropriate since the subject may have much less days since last visit compared to the targeted 28 days. In order to collect more accurate information for early terminated subjects, a modified version of EDE-QM 28 days version, named as EDE-QM 14-days look-up version, having a very similar rating scale as the regular EDE-QM, will be applied on early termination subjects who discontinue between 12 and 24 days, inclusive, following the previous administration of the EDE-QM. For those who discontinue more than 24 days following the previous visit, the regular EDE-QM (28 day lookback version) is administered. Data collected by using EDE-QM 14-days look-up version and regular version (ie, 28 days look-up version) will be summarized together.

